Aim 1. Determine impact of DOMS pain on demand for alcohol and marijuana and examine race and sex as moderators of this relationship.

We predict that those who undergo the DOMS induction paradigm will show greater increases in alcohol and marijuana demand than participants in the sham DOMS control group. We also predict an interactive effect of race and sex on DOMS-related changes in alcohol and marijuana demand, such that increases may be greater in White men than Black women and men, as well as White women.

Aim 2. Identify psychosocial factors associated with change in demand for alcohol and marijuana after DOMS induction.

Consistent with current evidence,^{42, 67} we predict that pain-related negative affect will mediate the association between DOMS-related pain and increased demand for alcohol and marijuana. We also predict that greater expectancy of analgesia from marijuana or alcohol use, higher negative urgency, and history of self-medication behaviors will predict greater change in alcohol and marijuana demand.

6. Research Plan:

Participants

We will recruit participants aged 21 years and older who are regular co-users of alcohol and marijuana (i.e., concurrent or simultaneous use at least 2-3 times per week over the past 6 months). Extent of co-use will be determined using the Alcohol Use Disorders Identification Test (AUDIT) and Cannabis Use Disorder Identification Test, Revised (CUDIT-R). A research team member will inform participants of inclusion and exclusion criteria via email or the phone. If an individual believes they meet all study criteria, they will be scheduled for the first study session (see Phone and Email Scripts for details). We will review all inclusion and exclusion criteria one additional time with participants before initiating the Informed Consent process.

Inclusion/Exclusion Criteria

Detailed inclusion/exclusion criteria are provided in Table 1.

Table 1. Inclusion and exclusion criteria
Inclusion Criteria 
• Aged 21-65 years;• English-speaking• Self-identify as White/Caucasian or Black/African American• Own a smartphone with cellular/data plan• Regularly co-use alcohol and smoked marijuana as indicated by scores of ≥ 3 on item 1 of the CUDIT-R and AUDIT.• Willing and able to give informed consent

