Participants who continue to qualify following completion of screening procedures and agree to proceed will be assigned to either the *DOMS* or *Sham DOMS* group. Assignments will be made according to a participant's unique subject identifier using a spreadsheet listing group assignment in pseudo-random order using the Excel random number function.

Participants will then complete the Alcohol Purchase Task (APT), Marijuana Purchase Tasks, (MPT), and DOMS or sham DOMS induction procedures. They will also be will be scheduled for a second lab session 48 hours later so that potential changes in DOMS-associated alcohol and marijuana demand can be investigated. Participants who complete the screening but either do not qualify or decide not to proceed will be paid \$15 via gift card. Those who do qualify and proceed with the study will be paid \$50 at the end of the first lab visit and \$15 at the end of the second lab visit. For the daily surveys, compensation was provided as a function of the number of surveys completed, with a maximum of \$30 for participants who completed 5/7 or more of their assessments (see "Daily Measures" section for additional information). We will also ask whether their DOMS (if any) has resolved with the daily measures. Additionally, participants who refer an individual to the study that attends the screening session will also receive \$20 per person referred. The referee(s) will be responsible for contacting the study team via phone or email in order to schedule the session. The referrer will receive the \$20 bonus once the person they refer attends their screening session, whether or not they eventually decide to participate. All participants who provide informed consent will be eligible to refer participants to the study regardless of whether they qualify to proceed after screening procedures.

Alcohol Purchase Task (APT) and Marijuana Purchase Tasks (MPT)

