Both the APT and MPT will be administered on REDCap during the first lab session prior to DOMS induction and during the second lab session (48 hours post DOMS induction). In the APT, participants are provided with a set of instructions, including a definition of a standard drink, and asked how many standard drinks they would consume at 21 prices, ranging from free to \$30/drink (e.g. "How many drinks would you consume if they were \$1.00 each?"). Procedures for the MPT are virtually identical, except a standard definition of the number of hits of marijuana in one joint is provided, and participants are asked how many hits of marijuana they would take at a series of escalating price points ranging from free to \$10/hit. Participants will also complete an adapted form of the MPT that allows for differences in preference for various marijuana-based products and modes of administration. From these data, the following indices of alcohol and marijuana demand will be generated: intensity (consumption of hits/drinks when free); breakpoint (the first price at which consumption was zero); O_{max} (maximum expenditure on alcohol and marijuana hits); P_{max} (price where demand becomes elastic); elasticity (rate of change in consumption with changes in price). Studies have demonstrated that these indices can be reduced to two latent factors: persistence (maintaining consumption despite increasing price) and amplitude (maximum consumption and price levels). Persistence is composed of elasticity, P_{max} , breakpoint, and O_{max} , while amplitude is composed of intensity and O_{max} .⁸⁵⁻⁸⁶

Isometric Strength Testing and DOMS Induction

Maximum voluntary contraction (MVC) of elbow flexion strength will be tested using a BiodeX System Isokinetic Dynamometer (BiodeX Medical Systems, Shirley, NY), and torque values obtained from this testing will be used to inform exercise protocols. The participant will first be seated within the testing apparatus with a stabilizing strap attached proximal to the elbow joint. The participant will then move through their available range of motion in the elbow flexion and extension. The device will be locked at 90 degrees of elbow flexion, and the participant will be instructed to build maximal flexion force while holding onto the grip handle of the machine. Once peak effort is achieved, the participant will be instructed to relax, the device will be released, and the subject will be returned to a neutral position.

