Hypotheses for DOMS-related changes in alcohol and marijuana demand indices (persistence and amplitude) will be assessed using separate 2 (group: DOMS vs. sham DOMS) x 2 (sex: men vs. women) x 2 (race: White vs. Black) x 2 (time: visit 1 vs. visit 2) repeated measures analysis of variance (ANOVA). Identical ANOVAs will examine changes in marijuana demand indices.

Aim 2: Identify psychosocial factors associated with change in demand for alcohol and marijuana after DOMS induction.

To test the hypothesis that negative affect mediates the relationship between DOMS pain and increased alcohol and marijuana demand, Pearson correlations will be conducted to examine continuous relationships between measures of pain, pain-related negative affect (e.g. pain experience VASs), and change in alcohol and marijuana demand. A series of linear regressions will then be conducted to examine 1) the effect of group (DOMS vs. sham DOMS) on change in alcohol and marijuana demand, and 2) the effect of group and pain-related negative affect on change in alcohol and marijuana demand. We will test the significance of indirect effects of pain-related negative affect using PROCESS, a custom macro in SPSS.

To examine the hypothesis that greater expectancy of analgesia from marijuana or alcohol use, higher negative urgency, and history of self-medication behaviors will predict greater change in demand, a simultaneous multiple linear regression analysis will be conducted with these variables as predictors in the model.

Power Analysis

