Effect size estimates for this study were derived from an interim analysis of data from an ongoing pilot project that examined the effect of DOMS on alcohol demand (N=40). In our pilot work, alcohol demand was assessed using the Alcohol Purchase Task (APT) before and after DOMS induction. Amplitude and persistence were derived from APT data using principal components analysis,⁸³⁻⁸⁴ and these factors explained approximately 89% of the variance in alcohol demand metrics. Changes in amplitude and persistence were examined using separate 2 (group: sham vs. DOMS) x 2 (time: time 1 vs. time 2) x 2 (sex: men vs. women) repeated measures ANOVAs. Results indicated sex x group x time interactions for both factors, such that DOMS tended to increase amplitude in men and decrease amplitude in women, $F(1,36)=3.13$, $p=.09$, partial eta squared=.08. A similar pattern of effects was found for persistence where DOMS decreased persistence in women and increased persistence in men, $F(1, 36) = 14.55$, $p=.001$, partial eta squared=.29. With power analyses conducted in G*Power ($\alpha=.05$, power=.80, correlation between repeated measures=0.5), we expect that a proposed sample size of 56 participants will be sufficient to achieve the objectives of the proposed research and have adequate sensitivity to detect medium between-group and interactive effects for which we do not have preliminary data.

7. Possible Discomforts and Risks:

Psychological Discomforts and Risks. Participants may be reminded of unpleasant emotions or experience negative thoughts or bodily sensations while reporting aspects of their current psychosocial functioning or medical history. To mitigate this risk, all participants will be informed they can withdraw from the study at any time or skip individual questions that may be upsetting to them.

Induction of Muscle Pain using Exercise: There is a low risk that exertional rhabdomyolysis (breakdown of muscle tissue due to damage) and myoglobinuria (a large amount of muscle proteins in the urine) may occur following eccentric exercise. However, research suggests that this occurs primarily if a person had not consumed enough fluids before multiple muscle groups are exercised eccentrically.⁸⁷⁻⁸⁸ We will address this risk by instructing participants to remain well-hydrated 24 hours prior to DOMS induction.

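### Aim 1's two-visit ANOVA is a valid change-score analysis, but visit-1 demand as a covariate would usually test the same group effects more precisely, and the White-men prediction has no follow-up rule.

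*Combined protocol and SAP*

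**What the plan says.** All references are to the combined protocol and SAP.

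- **Section 6, Data Analysis Strategy, Aim 1.** Each demand factor (persistence, amplitude) is analysed by group crossed with "2 (sex: men vs. women) x 2 (race: White vs. Black) x 2 (time: visit 1 vs. visit 2) repeated measures analysis of variance", and the marijuana factors in the same way. Visit 1 is a level of time, not a covariate.
- **Section 6, Data Analysis Strategy, Aim 2.** The mediation regressions examine "the effect of group (DOMS vs. sham DOMS) on change in alcohol and marijuana demand". They also use change, without visit-1 demand.
- **Section 6, Alcohol Purchase Task (APT) and Marijuana Purchase Tasks (MPT).** The tasks are "administered on REDCap during the first lab session prior to DOMS induction and during the second lab session", so the visit-1 score is taken before treatment.
- **Section 6, Screening Measures.** Assignment is made "using a spreadsheet listing group assignment in pseudo-random order using the Excel random number function".
- **Section 5, Aim 1.** The plan predicts "an interactive effect of race and sex on DOMS-related changes in alcohol and marijuana demand", in the sense that "increases may be greater in White men than Black women and men, as well as White women". The analysis section names no comparison to follow the four-way term.

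**The concern.** There are two gaps.

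First, a change score fixes the weight on the visit-1 value at one. A covariate model estimates that weight from the data. When the measure before treatment is unaffected by treatment and assignment is random, both approaches target the same group effect, and the covariate model usually has the smaller error. With 56 people in eight cells, and a pilot amplitude effect that the planned test would detect with power of only about .58, precision matters.

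Second, the section 5 prediction has a direction: White men above each of three other groups. The group x sex x race x time term has none. Without a stated follow-up, a significant four-way result could be reported as support for a White-men claim that the pattern of effects does not show.

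**Working it through.** **Inputs.** From Power Analysis: 56 participants, alpha .05, power .80, correlation between visits 0.5, and pilot sex x group x time effects with partial eta squared .08 (amplitude) and .29 (persistence). Assumed, because the documents do not say: 1:1 allocation, balanced cells (56/8 = 7), no dropout, and equal SDs unless varied below. The real visit correlation is not given. Section 4 calls test-retest reliability good without a figure, so .5 to .95 is shown.

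**The plan's 56.** The G*Power within-between formula is lambda = f²·N·m/(1−rho). With f² = .08/.92 = .0870, m = 2, rho = .5 and eight groups (7 numerator df), it needs N = 49, which rounds up to 56 as a multiple of 8. The match is not unique, since the plan does not name the test or the effect entered.

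**Step 1: the ANOVA terms are change-score tests.** On one simulated data set, the group x time t from the ANOVA and the group t for change were both 3.230. The four-way t and the three-way t for change were both 0.210.

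**Step 2: same group contrasts.** Over 4,000 simulated trials (rho .5), the mean group effect was 0.601 with change and 0.598 with the covariate (truth 0.6). Group x sex was 0.511 and 0.505 (truth 0.5). This does not extend to terms without group: with a pre-existing sex difference of 1 SD, the sex term was 0.01 with change and 0.50 with the covariate.

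**Step 3: size of the gain.** With visit SDs s1 and s2,

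- Var(change) = s1² + s2² − 2·rho·s1·s2
- Var(visit 2 given visit 1) = s2²(1 − rho²)
- difference = (s1 − rho·s2)², never negative.

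With equal SDs the ratio is (1 + rho)/2. Estimating the slope costs one error df (48 to 47) and multiplies the variance by about 1 + 1/46 = 1.022. For the group effect, lambda = d²·56/4 = 14d², and the planned test reaches .80 at d = 0.764 SD of change. For the amplitude term, lambda = 56 × .08/.92 = 4.87; the correlation is already contained in the pilot's partial eta squared. With the covariate, lambda is divided by the net ratio.

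| rho | (1+rho)/2 | net ratio | 56/net ratio | power .80 becomes | amplitude term, .58 becomes |
|---|---|---|---|---|---|
| .5 | .750 | .766 | 73 | .89 | .69 |
| .8 | .900 | .920 | 61 | .83 | .62 |
| .9 | .950 | .971 | 58 | .81 | .59 |
| .95 | .975 | .996 | 56 | .80 | .58 |

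The gain is therefore about 17, 5, 2 and 0 participants, and breaks even where (1 + rho)/2 × 47/46 = 1, at rho = .957. Simulation (20,000 runs, chance baseline imbalance included) agrees: .798 becomes .889, .831 and .810 at rho .5, .8 and .9, with type I error .050. The persistence term is already above .99, so nothing is gained there.

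Unequal SDs, rho .8, s2/s1 = 1.25: Var(change) = 1 + 1.5625 − 2 = .5625, and the conditional variance is 1.5625 × .36 = .5625. The ratio is 1.000 and only the cost remains; simulated power goes from .799 to .790.

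**Step 4: Aim 2.** On one simulated data set the group coefficient was 0.759 for change alone and 0.807 with the covariate. Adding visit-1 demand to the change regression also gave 0.807.

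**Step 5: direction.** The four-way contrast is the DOMS-minus-sham effect in White men − Black men − White women + Black women. Effects of 1, 0, 0, 0 give 1. Effects of 1, 0, 0, 1 give 2, although White men then do not exceed Black women. With 7 per cell and effects of 1.5, 0, 0, 1.5 SD of change, the term is significant with probability about .785.

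A rule that requires a significant interaction and White men above each other group (each comparison at two-sided .05) succeeds, with change scores and only White men responding, with probability about .04 at 1.0 SD and .14 at 1.5 SD.

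**The case against.** The planned ANOVA tests what section 5 says, greater increases with DOMS than with sham, and extends the pilot's own analysis. That stands: a reader might infer that the ANOVA is wrong or biased, and nothing in the documents supports this.

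The gain is conditional. A reader who divides 56 by (1 + rho)/2 alone gets 74.7, 62.2 and 58.9, which leaves out the cost of the slope. The largest gain rests on rho .5, a planning input; at .8 to .9 it is only one to three points of power.

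A reader might also infer that Aims 1 and 2 conflict. They do not: both now analyse change. A mismatch would arise only if Aim 1 were changed alone.

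Nor does the four-way term fail to test the prediction's first clause. It might be argued that it misses additive race and sex effects that still leave White men highest. But section 5 predicts an interactive effect, and additive effects contain none, so a null four-way result is then the right answer. For the same reason the three comparisons alone are not enough: under additive effects of 3, 1.5, 1.5, 0 they would all succeed with probability .33, whereas a rule that also requires the interaction cannot exceed that term's .05. Pooling the other three groups into one contrast does not help either: a sex-only effect at eta squared .29 makes it significant with probability .77.

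**Conclusion.** The planned Aim 1 analysis is valid. The covariate model is a cheap improvement that should be made, not the correction of an error. At 56 participants it is worth about 17, 5 or 2 participants at rho .5, .8 or .9, almost nothing near .95, and about minus one point of power at rho .8 with an SD ratio of 1.25. The figures rest on 1:1 allocation, balanced cells, equal SDs except where varied, and no dropout. They also assume that visit-1 answers are not influenced by knowing the assignment, since the plan describes assignment and then says "Participants will then complete the Alcohol Purchase Task (APT), Marijuana Purchase Tasks, (MPT), and DOMS or sham DOMS induction procedures". The benefit is limited to terms that contain randomised group; sex and race differences in change are a different question under adjustment.

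The second gap is one of interpretation. The four-way term tests the predicted interaction but not its direction, and no follow-up is named. The prediction is hedged and can be tested only weakly here, so the plan should say what would count as support.

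**What to change.** 1. **Aim 1.** For each alcohol and marijuana demand factor, fit the visit-2 score on visit-1 score, group, sex, race and their interactions. Keep group, group x sex, group x race and group x sex x race as the planned tests. In the pilot, "alcohol demand was assessed using the Alcohol Purchase Task (APT) before and after DOMS induction", so its visit correlation and SD ratio can show the likely gain for alcohol.
2. **Aim 2.** Add visit-1 demand as a covariate in the group and PROCESS models. Change may stay as the outcome, because the group coefficient is then identical to Aim 1's when the other terms match. Expectancy, negative urgency and self-medication history are not randomised, so adjustment changes the question there; state which is meant.
3. **White-men prediction.** Report the DOMS-minus-sham effect with 95% CI in each sex-by-race group. Claim the prediction for a factor only if the interaction is significant and the effect in White men exceeds that in each of the other three groups, each at two-sided .05. Otherwise report the four effects as descriptive. State that power for this claim is very low, with the .04 and .14 above.

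**Cost.** Analysis wording and a few lines of SPSS syntax, no new data, and one degree of freedom per model. Over four factors, item 3 adds 16 group effects and 12 pairwise comparisons. It does not settle multiplicity across factors.

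### The pilot shows DOMS moving alcohol demand in opposite directions in men and women, but the Aim 2 group and mediation models contain no sex term

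*Combined protocol and SAP*

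**What the plan says.** The Power Analysis section reports the only preliminary data, from an interim look at "an ongoing pilot project that examined the effect of DOMS on alcohol demand (N=40"). It found sex x group x time interactions for both demand factors. For persistence, "DOMS decreased persistence in women and increased persistence in men": F(1,36)=14.55, p=.001, partial eta squared .29. Amplitude tended the same way: F(1,36)=3.13, p=.09, partial eta squared .08. Marijuana demand and negative affect are not reported.

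Under Specific Aims, Aim 1 predicts that "those who undergo the DOMS induction paradigm will show greater increases in alcohol and marijuana demand" than sham participants. It adds a race and sex interaction, described as increases that may be larger in White men than in the other three groups. The Aim 1 analysis (Data Analysis Strategy) is a group x sex x race x time repeated measures ANOVA.

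The Aim 2 analysis consists of Pearson correlations, a regression of change in demand on group, a regression for "the effect of group and pain-related negative affect on change in alcohol and marijuana demand", and a PROCESS test of the indirect effect. No sex term, stratum or moderator is named, and no PROCESS model is specified.

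**The concern.** The first Aim 2 regression estimates the DOMS-versus-sham effect on change in demand, which is the quantity that the pilot says changes sign between the sexes. A model with group but no sex estimates the average of the two effects. If they are of similar size, the average is near zero. The reversal also goes into the residual variance, so the test becomes less likely still to reach significance.

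A null Aim 2 group effect could then mean either no effect of DOMS or two opposite effects, and nothing in the Aim 2 models would tell these apart. A non-null pooled estimate would describe neither men nor women. The indirect effect is exposed in the same way, but only under a further condition set out below.

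**Working it through.** **Pilot figures.** From F on 1 and 36 df, partial eta squared = F/(F+36). F=3.13 gives .080 and p=.085; F=14.55 gives .288 and p=.0005. These agree with the printed values apart from rounding of the second p. The planned N of 56 can be matched under one set of G*Power inputs (within-between interaction, 8 cells, f=0.295 from eta squared .08, minimum 49 rounded up to a multiple of 8). The text does not state those settings, so the match is inferred.

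**Size of the reversal.** Assume 10 pilot participants per sex-by-group cell and express change scores in within-cell SDs. The difference between the sexes' DOMS effects is D = sqrt(F x 4/10).
- Persistence: sqrt(14.55 x 0.4) = 2.41, or +1.21 and -1.21 if split evenly.
- Amplitude: sqrt(3.13 x 0.4) = 1.12, or +0.56 and -0.56 if split evenly.

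The pilot gives no sex-specific effects, so the split is an assumption. An even split is the worst case for the pooled test.

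**Aim 2 regression of change on group, N=56.** Assume 28 per arm and 14 per sex-by-arm cell. Simulated chance of significance at two-sided .05:

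| Men / women (SD) | Group only | Sex x group if added |
|---|---|---|
| +1.21 / -1.21 | 1% | 99% |
| +0.56 / -0.56 | 3% | 53% |
| +1.61 / -0.80 | 13% | 99% |
| +0.75 / -0.37 | 8% | 53% |
| +2.41 / 0 | 97% | 99% |
| +1.12 / 0 | 47% | 53% |

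The rate can fall below 5% because the omitted reversal inflates the residual. For +/-1.21 the DOMS-arm variance is 1 + 1.21² = 2.46, so the average over arms is (1 + 2.46)/2 = 1.73. The standard error is then too large by sqrt(1.73) = 1.32. If sex were not balanced across arms, the rate would drift up towards the nominal 5%, which is still only chance.

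**Aim 1 ANOVA, same assumptions, race terms ignored (48 df).** Power for sex x group x time is D/sqrt(4/14) referred to the noncentral t: 0.99 for persistence and 0.54 for amplitude. Each within-sex contrast at an even split has power 0.88 (persistence) or 0.31 (amplitude). The group x time term has power .05 at an even split, and 0.31 at 2:1 for persistence.

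**Mediation (bootstrap simulation, N=56, group raises negative affect by 1 SD in both sexes).**
- Affect-to-demand slope +0.5 in men and -0.5 in women: pooled indirect effect about 0, detected in about 4% of runs, against about 48-50% within each sex.
- Slope +0.6 in men and -0.3 in women: pooled indirect effect detected in 12% of runs; the men-women difference in 70%.
- Slope +0.5 in both sexes, with the same reversal carried by the direct path: pooled indirect effect about 0.50, detected in about 73% (persistence-sized) to 88% (amplitude-sized) of runs.

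**The case against.** A reader might infer that Aim 1 is also blind to the reversal, so that the trial would conclude that pain has no effect on demand. The documents do not support that. Aim 1 names sex as a moderator, and its only analysis tests sex x group x time, with power about 0.99 for a persistence-sized reversal. Such a conclusion would require ignoring a planned test. What is left for Aim 1 is the wording of the prediction, which speaks of increases throughout while the pilot shows decreases in women. The F tests are non-directional, so that wording changes no analysis.

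A reader might also infer that mediation must cancel. It need not. The pilot reports no negative-affect data, and a reversed total effect does not imply a reversed affect-to-demand path. If the reversal lies in the direct path, the planned PROCESS test still finds the indirect effect in most runs. The cancelling case is one assumed scenario.

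It is also fair to say that the pilot is an interim result in 40 people, covers alcohol only, and is suggestive rather than clear for amplitude. If women's effect were zero rather than reversed, the pooled test would keep most of its power for persistence. These points limit the size of the concern. They do not supply the missing sex term in Aim 2.

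**Conclusion.** The point holds for Aim 2 and is a cheap improvement rather than a flaw that invalidates the plan. The protocol's own pilot gives a reason to expect the group effect on alcohol demand to differ in sign by sex, and the Aim 2 group and mediation models cannot show it. With an even split, the group-on-change regression would be significant in about 1-3% of trials despite real effects within each sex; with a 2:1 split, in about 8-13%. These figures rest on pilot cells of 10, arms of 28 balanced by sex, and assumed splits. Loss of the pooled indirect effect needs the further assumption of a sex-reversed affect-to-demand path. For Aim 1 the fault is confined to a prediction of increases that does not match the pilot in women, and to the absence of a statement on reading group x time when the sex interaction is present. For marijuana demand there is no pilot evidence either way.

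**What to change.** In the Data Analysis Strategy, Aim 2:
- Add sex and group x sex to the regressions of change in demand.
- Beside the pooled mediation, report a moderated mediation that includes negative affect x sex, with the indirect effect for men and for women and the index of moderated mediation.

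In the Data Analysis Strategy, Aim 1, add one sentence: the group x time term is read together with sex x group x time and the within-sex DOMS-versus-sham contrasts.

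In Specific Aims, acknowledge that the pilot showed a decrease in alcohol persistence in women. Do not commit the marijuana or amplitude hypotheses to a direction in women on the strength of an alcohol-only pilot.

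No new data or participants are needed. The cost is a few more parameters and imprecise sex-specific results. With about 28 people per sex, a sex-specific indirect effect has roughly 50% power at a slope of 0.5, and a within-sex contrast has about 0.31 for an even-split amplitude-sized effect. Report them as estimates with intervals, and do not read a non-significant result within one sex as absence of effect.
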